11.7.3 Retention of Documents

The investigator must maintain source documents for each patient in the study, consisting of all demographic and medical information, including laboratory data, x-ray, etc., and keep a copy of the signed informed consent form. All information on case report forms must be traceable to these source documents in the patient's file. Data without a written or electronic record will be defined before trial start and will be recorded directly on the case report forms, which will be documented as being the source data.

11.8 Disclosure of Information

All information provided to the investigator by Ampio Pharmaceuticals, Inc. or their designee, will be kept strictly confidential. No disclosure shall be made except in accordance with a right of publication granted to the investigator.

No information about this study or its progress will be provided to anyone not involved in the study other than to Ampio Pharmaceuticals, Inc., or its authorized representatives, or in confidence to the IRB, or similar committee, except if required by law.

11.9 Discontinuation of the Study

It is agreed that, for reasonable cause, either the investigator or Ampio Pharmaceuticals, Inc., may terminate the investigator's participation in this study after submission of a written notice. Ampio Pharmaceuticals, Inc., may terminate the study at any time upon immediate notice for any reason, including the Sponsor's belief that discontinuation of the study is necessary for the safety of patients.

11.10 Study Report, Publication Policy and Archiving of Study Documentation

11.10.1 Study Report and Publication Policy

An ICH-compliant integrated clinical and statistical report will be prepared upon completion of the study and data analysis. The results of the study will be published in a relevant peer-reviewed journal, with authorship status and ranking designated according to the acknowledged contributions of participating investigators, institutions and the Sponsor.

11.10.2 Study Documents

The investigator must maintain source documents for each patient in the study, consisting of all demographic and medical information, questionnaires, including laboratory data, MRI (as applicable), etc., and keep a copy of the signed informed consent form. All information on the e-case report forms must be traceable to these source documents in the patient's file. Data without a written or electronic record will be defined before trial start and will be recorded directly on the e-case report forms, which will be documented as being the source data.

11.10.3 Archiving of Documents

Essential documents, as listed below, must be retained by the investigator for as long as needed to comply with national and international regulations. The Sponsor will notify the investigator(s)/institution(s) when the study-related records are no longer required. The investigator agrees to adhere to the document retention procedures by signing the protocol. Essential documents include:

- IRB/IEC/REB approvals for the study protocol and all amendments
- All source documents and laboratory records
- CRF copies (electronic copies on a CD-ROM)
- Patients' informed consent forms (with study number and title of trial)
- FDA form 1572
- Any other pertinent study document

## **1. INTRODUCTION**

This statistical analysis plan (SAP) outlines the proposed statistical methods to be implemented during the review of data to ensure that it confirms with categories determined by the CRF or the anticipated ranges for continuous variables and analysis of data collected within the scope of Ampion Protocol AP-013, “A Randomized, Controlled, Double-Blind Study To Evaluate The Efficacy And Safety Of An Intra-Articular Injection Of Ampion™ In Adults With Pain Due To Severe Osteoarthritis Of The Knee,” dated 7 June 2019.

It is not intended that each and every table, listing, or graph will be included in the clinical study report (CSR). It is also possible that additional analyses will be conducted after review of the data. Any analyses or summaries not specified in the SAP, but performed after review of the data, will be identified in the CSR as post hoc.

## **2. OBJECTIVES**

### **2.1 Primary Objectives**

The co-primary trial objectives are to evaluate the greater efficacy for pain improvement and functional improvement of 4 mL Ampion versus saline IA injection when applied to patients suffering from severe OAK. Efficacy will primarily be assessed with WOMAC A pain and WOMAC C function scores.

Mean change in the WOMAC A weekly pain scores from Baseline to Week 12 will be compared between Ampion and saline control. Mean change in WOMAC C function score from Baseline to Week 12 will be compared between Ampion and saline control. This will ensure that Ampion is superior to saline in improving pain and function.

### **2.2 Secondary and Exploratory**

The secondary trial objectives include the following evaluations of an intra-articular injection of Ampion, as compared to saline, when administered to patients suffering from severe OAK: assessment of safety; improvement in the Patient Global Assessment; improvement in pain utilizing a 100 mm VAS scale; the amount of rescue analgesia.

Primary and secondary objectives will be reported by age subsets, race, and sex.

Exploratory objectives include analyzing the effect, if any, of the efficacy of Ampion, as compared to saline, on stiffness; Outcome Measures in Rheumatology Clinical Trials and Osteoarthritis Research Society International (OMERACT-OARSI) responder status; proportion of treatment failures; and change in pain and function as a cumulative distribution function (CDF) plot.

Analysis with biomarkers, such as those for analgesic use and chemokines and cytokines associated with inflammation and cartilage regeneration, may be analyzed to compare differences between treatment groups using urine samples collected at Week 12.

Additionally, a Bayesian meta-analysis will be performed for WOMAC A pain sub score using all KL 4 patients in studies AP-003A, AP-003-B, AP-003-C, AP-004, and AP-013.

### **2.3 Study Design**

This is a randomized, saline-controlled, double-blind study with a 28-day screening period for each patient followed by a 24-week participation period. This trial will use an adaptive design with promising zone method for sample size re-estimation at the interim analysis.

The clinical effects of treatment on severe OAK will be evaluated at baseline 2, 4, 6, 8, 10, 12, and 24 weeks, using the Western Ontario and McMaster Universities Arthritis Index (WOMAC®) osteoarthritis Index 3.1, and the Patient's Global Assessment of disease severity (PGA).

Daily assessments of WOMAC A score using a subject diary will be assessed for seven days beginning one week prior to the clinic visits at Week 0 (baseline) and Week 12 to allow for calculation of a weekly average of WOMAC A Daily Pain scores, which will be used for conducting the primary efficacy analysis.

The WOMAC® is a validated pain scoring system and sets the standard for the patient response. In order not to bias the collection of data, only questions from the validated WOMAC pain scale will be asked of patients. Clinical meaningfulness will be determined by the end results of this trial, specifically by the apparent clinical benefit versus any adverse events or any increased apparent risk. Safety will be assessed by recording adverse events (through 24 hours post-dose and at all follow up contacts) and physical examination and vitals (Baseline, Weeks 6, 12 and 24).

### **2.4 Sample Size**

This trial will use an adaptive design with promising zone method for sample size re-estimation.

This trial is designed for 1,034 patients, 517 per study arm, randomized 1:1 for Ampion and saline IA injection. There will be an interim analysis when at 724 patients, 362 per study arm, have completed their Week 12 visit.

A promising zone analysis will be performed at the interim. Following the interim analysis, enrollment will either a) continue up to a total of 1034 patients, 517 patients per study arm, randomized 1:1 for Ampion and saline IA injection; b) allow for sample size re-estimation up to a maximum of 1.5 times the original trial size for a total of 1,552 patients, 776 per study arm, randomized 1:1 for Ampion and saline IA injection.

The Ampion effect was estimated as the average change in pain from Baseline to Week 12 for KL 4 subjects receiving Ampion from all prior single injection studies randomized 1:1 with saline control. Saline effect was estimated as the average change in pain from Baseline to Week 12 for KL 4 subjects receiving saline from all prior single injection studies randomized 1:1 for Ampion and saline. The sample size for assessing the WOMAC A Pain score alone would be 690 total patients for 90% power.

The Ampion effect was estimated as the average change in function from Baseline to Week 12 for KL 4 subjects receiving Ampion from all prior single injection studies randomized 1:1 with saline control. Saline effect was estimated as the average change in function from Baseline to Week 12 for KL 4 subjects receiving saline from all prior single injection

studies randomized 1:1 for Ampion and saline. The sample size for assessing the WOMAC C Function score alone would be 984 patients for 90% power.

The total sample size is chosen as the larger of the two values. To be conservative sample sizes were estimated with a 5% dropout so 1,034 patients will be enrolled to achieve 984 total patients. All ITT patients will be included in the statistical analysis. At the assumed effect size there is a 90% probability of success at 1,034 patients.

The study design of 1,034 total patients achieves 97% power assuming a WOMAC A pain score with mean pain decreases of -0.83 for Ampion and -0.62 for saline and a standard deviation of 0.85.

### **3. STUDY ENDPOINTS AND COVARIATES**

#### **3.1 Primary Endpoints**

The trial will test whether Ampion can produce a superior improvement in pain vs. saline control and a superior improvement in function vs. saline. This goal is achieved using two co-primary endpoints:

Change in the WOMAC A weekly pain sub score between Baseline and Week 12  
Change in WOMAC C physical function sub score between Baseline and Week 12

An average of the daily WOMAC A pain assessments will be used to calculate the weekly pain score, at baseline and at Week 12.

Mean 12-week change in the WOMAC A pain score will be compared between Ampion and saline control. Mean 12-week change in WOMAC C physical function score will be compared between Ampion and saline control.

#### **3.2 Secondary Endpoints**

- Change in PGA between Baseline and Week 12
- Change in 100mm VAS Pain scale between Baseline and Week 12
- Use of rescue analgesia (amount of acetaminophen used between Baseline and Week 12)
- Incidence and severity of treatment-emergent adverse events (TEAEs)

#### **3.3 Exploratory Endpoints**

- Change in WOMAC B stiffness sub score between Baseline and Weeks 2, 4, 6, 8, 10, 12, and 24
- Response status based on the OMERACT-OARSI criteria at Weeks 2, 4, 6, 8, 10, 12, and 24
- Proportion of treatment failures at Week 12
- Change in pain and function analysis as a cumulative distribution function (CDF) plot
- A Bayesian meta-analysis for WOMAC A pain sub score including KL 4 patients from studies AP-003-A, AP-003-B, AP-003-C, AP-004, and AP-013

- Change in WOMAC A pain sub score between Baseline and Weeks 2, 4, 6, 8, 10, and 24
- Change in WOMAC C function sub score between Baseline and Weeks 2, 4, 6, 8, 10, and 24
- Change in WOMAC A pain sub score between Baseline and Weeks 2 through 12 and Weeks 2 through 24
- Change in WOMAC C function sub score between Baseline and Weeks 2 through 12 and Weeks 2 through 24
- Change in PGA between Baseline and Weeks 2, 4, 6, 8, 10, and 24
- Change in WOMAC C physical function sub score between Baseline and Weeks 2, 4, 6, 8, 10, 12, and 24
- Difference in urine analysis between treatment groups at Week 12

### **3.4 Covariates**

Analyses of change will include treatment assignment, Week, and the Baseline measure of the variable being analyzed as a covariate in the model.

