3.3 Safety Monitoring Committee

A Safety Monitoring Committee (SMC) will be established to review the safety of Ampion as the study progresses. The SMC will consist of independent clinicians and statisticians not involved in the conduct of the clinical trial. The Medical Monitor will attend open sessions of the SMC meetings. The SMC will be primarily responsible for reviewing any serious Adverse Event (SAE) and other clinically important safety findings (e.g., discontinuations due to AEs) that may occur during the study. Prior to unblinding any treatment assignments, a charter will be developed to detail the SMC review responsibilities, the frequency of meetings, and data evaluation plans.

A promising zone analysis will be run after outcomes are available for 724 patients (70% of final sample size). The promising zone analysis will be run for WOMAC C since function will be the predominant determinant of sample size.

The SMC, with the exclusion of the Medical Monitor, will also be tasked with evaluating whether sample size increase criteria has been met for the interim efficacy analysis. The SMC committee will review the interim analyses and report the next steps to the Sponsor, which will include one of the following prespecified actions: (1) continue to a total of 1,034 patients, 517 patients per study arm, randomized 1:1 for Ampion and saline IA injection; (2) sample size re-estimation up to 1.5 times the original trial size for a total of 1,552 patients, 776 per study arm, randomized 1:1 for Ampion and saline IA injection, has occurred using the promising zone and the new sample size will be reported.

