5.1 Description of Study Visits

5.1.1 Visit -1 (Day -28 through Day 0, in-clinic): Screening

The following procedures will be performed:

- Obtain written informed consent before the start of any study specific procedure.
- Review medical history including all previous treatments for OA
- Record prior and concomitant medications including start/stop dates, indication, dose and frequency
- Record demographic data including year of birth, age, gender and race
- Measure and record height and weight
- Perform and record physical examination
- Record KL Grade from radiological assessment that is not older than 6 months prior to screening. Patient may have an x-ray at screening in order to satisfy this requirement
- Record pain in the index knee with the WOMAC Index 3.1 using both the 5-point Likert scale and the 100mm VAS scale
- Record pain in the contralateral knee with the WOMAC Index 3.1 pain subsection using both the 5-point Likert scale and the 100mm VAS scale
- Record vital signs. (Measure body temperature, systolic blood pressure [SBP], diastolic blood pressure [DBP] and pulse rate)
- Evaluate all inclusion and exclusion criteria to ensure that patients meet all inclusion criteria and none of the exclusion criteria
- Review collection instructions of daily diary pain scores with subject

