6.1.2 Patient's Global Assessment of Disease Severity (PGA)

The PGA should be completed by patients at Screening, pre-dose Day 1 (prior to injection), and at Weeks 2, 4, 6, 8, 10, 12 and 24.

Patients are asked the following question: "Considering all the ways in which your arthritis affects you, please indicate how you are doing."

Patients respond by using a 5-point adjectival Likert score (0 = Very Well, 1 = Well, 2 = Fair, 3 = Poor, 4 = Very Poor).

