6.2.1 Vital Signs

Vital signs (radial pulse rate, SBP, DBP, and body temperature) should be recorded at Screening, pre- and post-treatment Day 1, and then on visits at Weeks 6, 12 and 24.

Vital signs should be taken after the patient has rested in a seated position for at least five minutes.

Table 6.1 Schedule of Assessments and Procedures

	Screening	Pre-Baseline (phone)	Baseline	24-hours (phone)	Week 2 (phone)	Week 4 (phone)	Week 6	Week 8 (phone)	Week 10 (phone)	Pre-Week 12 (phone)	Week 12	Week 24	Early Term.
Assessments & Procedures	Visit -1 Day-28 to 0	Visit 0 Day -6 to 0	Visit 1 Day 0	Visit 2 Day 1	Visit 3 Day 14 ± 7	Visit 4 Day 28 ± 7	Visit 5 Day 42 ± 7	Visit 6 Day 56 ± 7	Visit 7 Day 70 ± 7	Visit 8 Day 77 ± 7	Visit 9 Day 84 ± 7	Visit 10 Day 174 ± 7	
Informed Consent	X												
Inclusion/exclusion criteria	X		X										
Medical history/prior medications	X		X										
Concomitant medications	X		X	X	X	X	X	X	X		X	X	X
Urine sample			X**								X		
Physical examination	X		X				X				X	X	X
Vital Signs	X		X				X				X	X	X
Randomization			X										
Review Diary Completion Instructions	X								X				
Phone Contact Daily Collection Reminder		X								X			
WOMAC A (Likert)	X	X*	X***		X	X	X	X	X	X*	X***	X	X
WOMAC A (VAS)	X	X*	X***							X*	X***		X
WOMAC B and C (Likert)	X		X		X	X	X	X			X	X	X
PGA	X		X		X	X	X	X			X	X	X
X-ray ¹	X												
Study treatment			X										
Dispense Rescue medication			X										
Review Rescue medication				X	X	X	X	X	X		X	X	X
Adverse Events			X	X	X	X	X	X	X		X	X	X

Visits are in clinic except for Day 1 and Weeks 2, 4, 8 and 10 when patients will be contacted by telephone

¹X-ray may be acquired at Screening to satisfy inclusion criteria, “Index knee must be symptomatic for greater than six months with a clinical diagnosis of OA and supported by radiological evidence (KL 4) that is not older than six months prior to the date of screening”.

*Patients will complete 7 daily pain score assessments up to and including the Baseline and Week 12 visits to allow calculation of WOMAC A weekly pain scores. The Screening and first Pre-Baseline daily pain score collection may occur on the same day, in office or at home, as appropriate.

**Urine will only be collected at Baseline if necessary to conduct a pregnancy test; collection to occur as applicable

***The WOMAC may occur in office or at home, and may serve as the 7th WOMAC Daily Pain collection

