10.3.4 Statistical Analysis of Co-Primary Effectiveness Endpoints

A mixed-effects model with repeated measures (MMRM) will be used to test the main effect of change in WOMAC A weekly pain score (determined as the average of Daily Pain measurements taken at Baseline and Week 12) from Baseline of Ampion vs. saline at 12 weeks. The model will include change from Baseline measures at 2, 4, 6, 8, 10, and 12 weeks. Treatment assignment, week, and Baseline WOMAC A measure will be included as fixed effects. Patient ID will be included to capture repeated measures using a compound symmetric covariance matrix for residuals. The primary hypothesis test for pain is the change in pain at 12-weeks at the one-sided $\alpha = 0.025$ level.

The same model will be used to test the effect of WOMAC C function change from Baseline of Ampion vs. saline at 12 weeks. WOMAC C will be tested at one sided $\alpha = 0.025$. Because both endpoints have to achieve statistical significance, this pairing ensures the one-sided Type I error control at the 0.025 level.

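### PGA, and WOMAC C if its Screening reading is really taken, are adjusted for one Day 0 reading only, which leaves a small gain in precision unused

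*SAP*

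**What the plan says.** - **Covariates.** SAP 3.4: "Analyses of change will include treatment assignment, Week, and the Baseline measure of the variable being analyzed as a covariate in the model". SAP 8.6.2 repeats this for PGA (treatment, week, Baseline PGA).
- **Meaning of Baseline.** SAP 5.2 takes the Day 0 value, with the last earlier screening-period value as a substitute if Day 0 is missing. Protocol 10.3.6 takes the latest pre-treatment value. Pain is the exception: Protocol 10.3.6 averages its daily scores over days -6 to 0.
- **Screening PGA.** Protocol 6.1.2: "The PGA should be completed by patients at Screening, pre-dose Day 1 (prior to injection" (the injection day, numbered Day 0 elsewhere). Protocol Table 6.1 and SAP 13 agree.
- **Screening WOMAC C.** In both schedule tables the row "WOMAC B and C (Likert") is marked at Screening and again at Baseline. Protocol 6.1.1 starts WOMAC B and C collection at Week 0, and the Screening list in Protocol 5.1.1 names only WOMAC pain. That list also omits PGA, which 6.1.2 requires, so it is not complete.
- **Function model.** SAP 8.6.1 and Protocol 10.4.1 name only Week as a fixed effect. Protocol 10.3.4 says the pain model, with treatment, week and baseline, also serves for function, and SAP 3.4 points the same way.
- **Role of function.** Protocol 3.3 runs the promising-zone analysis on WOMAC C because "function will be the predominant determinant of sample size". SAP 2.4: "The sample size for assessing the WOMAC C Function score alone would be 984 patients for 90% power", against "The sample size for assessing the WOMAC A Pain score alone would be 690 total patients for 90% power".

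**The concern.** Pain enters its model with a seven-day baseline mean, while function and PGA enter theirs with one questionnaire. A single reading carries day-to-day noise, so it removes less between-patient variance from the Week 12 comparison than two readings might. Function sets the sample size and alone drives the interim decision that can raise enrolment from 1,034 to 1,552. PGA comes first in the secondary testing sequence. If a second pre-treatment reading is already in the database, putting it in the model is a cheap way to narrow both confidence intervals.

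**Working it through.** **Inputs from the documents.** One-sided alpha 0.025; 90% power; 984 evaluable patients for function (492 per arm) and 690 for pain; pain difference 0.21 and SD 0.85; 1:1 allocation.

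**Assumed, because the documents give no value.** r is the correlation of one pre-treatment reading with Week 12 (0.4 to 0.6). ρ is the correlation between the two readings (0.7 to 0.8). The 984 is taken to give 90% power with the single Day 0 covariate in the model.

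**1. The plan's own figures.** Pain: n per arm = 2(1.960 + 1.2816)² × 0.85² / 0.21² = 344.3, so 345 per arm and 690 in total, as stated. Function: no effect or SD is given, so 984 cannot be rebuilt. Solving backwards, the standardised effect is 3.2415 × √(2/492) = 0.207. Power would be 91.4% if all 1,034 patients contributed.

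**2. Two equally predictive readings.** Residual variance is 1 − r² with one reading and 1 − 2r²/(1 + ρ) with two. Power at 984 is Φ(3.2415/√ratio − 1.96).

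| r | ρ | One reading | Two readings | Ratio | Equivalent N | Power at 984 |
|---|---|---|---|---|---|---|
| 0.4 | 0.8 | 0.840 | 0.822 | 0.979 | 964 | 90.6% |
| 0.4 | 0.7 | 0.840 | 0.812 | 0.966 | 951 | 91.0% |
| 0.5 | 0.7 | 0.750 | 0.706 | 0.941 | 927 | 91.6% |
| 0.6 | 0.8 | 0.640 | 0.600 | 0.938 | 923 | 91.7% |
| 0.6 | 0.7 | 0.640 | 0.576 | 0.901 | 887 | 92.7% |

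A 6,000-run simulation of the Week 12 contrast under compound symmetry, at r = 0.5 and ρ = 0.7, gave a ratio of 0.946 against 0.941 by formula.

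**3. Screening the weaker predictor.** With correlations r₀ (Day 0) and rₛ (Screening) with Week 12, R² = (r₀² + rₛ² − 2r₀rₛρ)/(1 − ρ²), and the ratio is (1 − R²)/(1 − r₀²). For r₀ = 0.5:

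| rₛ | ρ = 0.7 | ρ = 0.8 |
|---|---|---|
| 0.45 | 0.974 | 0.991 |
| 0.40 | 0.993 | 1.000 |
| 0.35 | 1.000 | not run |

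The gain is exactly nil when rₛ = r₀ × ρ, for example 0.40 = 0.5 × 0.8, which lies inside the assumed ranges. At rₛ = 0.45, power is about 90.7% (ρ = 0.7) or 90.3% (ρ = 0.8).

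**4. The form of the adjustment matters.** Suppose the covariate becomes the mean of the two readings while change is still taken from Day 0. With M = (1 + ρ)/2, residual variance is (2 − 2r) − (r − M)²/M. At r = 0.5 and ρ = 0.7, M = 0.85 and this is 1 − 0.1225/0.85 = 0.856, a ratio of 0.856/0.750 = 1.141 (simulation 1.137). Precision gets worse. Entering Day 0 and Screening as two separate covariates avoids this: with Day 0 in the model, the second covariate cannot raise residual variance beyond the loss of one degree of freedom.

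**5. PGA.** The documents give no effect size or power for PGA. The variance ratios carry over only if its correlations lie in the same ranges; no power figure can be given.

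**The case against.** The strongest objection is that the reading may not exist for the endpoint that matters most. Protocol 6.1.1 and 5.1.1 do not have WOMAC C at Screening; only the schedule tables do. If the text governs, using it would mean adding a questionnaire to the Screening visit. This stands, and it makes the WOMAC C part conditional. A reader might infer from the tables that precision is being given away at no cost on the binding co-primary; the documents are too inconsistent to support that. For PGA, text and tables agree.

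Second, equal predictive value is a favourable assumption. Screening can precede Day 0 by up to 28 days, and patients are selected on Screening pain of at least 1.5, which may restrict the range of Screening scores. This also stands: 2% is not a floor, and the gain can vanish.

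Third, the 90% starting point is uncertain. The 690 for pain comes from a formula with no covariate term. If the 984 was derived the same way, the planned Day 0 covariate already lifts power above 90%. This affects the power figures, not the variance ratios.

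Fourth, adjusting for the latest pre-treatment value is a valid prespecified choice. That is correct, and it limits the point to efficiency. It does not remove it, because a separate covariate has essentially no downside.

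Two further inferences fail. One is that the Screening values go unused: SAP 5.2 makes them the fallback for a missing Day 0 value. The other is that contralateral-knee pain should also be a covariate for function, since Protocol 5.1.1 has sites "Record pain in the contralateral knee with the WOMAC Index 3.1 pain subsection". No correlation or calculation supports this, and Protocol 4.3 recommends that this score be below 1.5, which narrows its range.

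**Conclusion.** The point holds as a modest missed efficiency. It is established for PGA and conditional for WOMAC C on the Screening reading being collected. Under the assumed correlations the saving in residual variance runs from nil to about 10%, and WOMAC C power lies between 90% and about 92.7%. In the middle case of equal predictors (r = 0.5, ρ = 0.7) the saving is about 6% and power 91.6%. None of the correlations comes from the documents. A reader should not take this as a flaw in the validity of the primary analysis: the comparison stays unbiased and type I error is unaffected. The incomplete function model in SAP 8.6.1 comes first, because a second covariate cannot be specified for a model whose treatment and baseline terms are not stated.

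**What to change.** 1. In SAP 3.4 and 8.6.2, prespecify Screening PGA as a second, separate fixed covariate beside Day 0 PGA. Do not average the covariate alone while change is still taken from Day 0.
2. State what happens when one of the two readings is missing. Under the SAP 5.2 fallback, a patient without a Day 0 value would otherwise have the Screening value entered twice.
3. Reconcile Protocol 5.1.1 and 6.1.1 with Table 6.1 and SAP 13 on whether WOMAC C is collected at Screening, and bring PGA in 5.1.1 into line with 6.1.2.
4. In SAP 8.6.1 and Protocol 10.4.1, write the function model out in full: treatment, week, treatment-by-week interaction and Day 0 baseline. If Screening WOMAC C is collected, add it there as a separate covariate, and also in the imputation model and the interim WOMAC C statistic.
5. Do not add contralateral-knee pain.

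The cost is SAP wording, corrected protocol visit and model text, and one degree of freedom per model. Protocol 10.3.10 calls for a final SAP before unblinding at the interim analysis, so the change can still be prespecified there. If Screening WOMAC C turns out not to be collected, only the PGA covariate and the repair of the function model remain.
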